6.0 SAFETY PARAMETERS

Safety assessments include adverse events/serious adverse events, visual acuity loss, slit lamp findings, and intraocular pressure. The reporting time period is from the day cross-linking is performed through the last through the last study visit.

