3.3 OUTCOME MEASURES

Effectiveness Outcome Measures

The following will be evaluated 6 months after the cross-linking procedure:

Primary effectiveness measure:
Change in CDVA

Secondary effectiveness measures:

Change in UCVA

Change in K_{\max}

Safety Outcome Measures

Safety will be evaluated by assessing the following:

Adverse events (AEs)

Serious adverse events (SAEs)

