6.1 DEFINITIONS OF ADVERSE EVENTS

An adverse event is any untoward and unintended sign, symptom or disease temporally associated with the use of an investigational drug or device, or other protocol-imposed intervention, regardless of the suspected cause. Conditions or diseases that are chronic but stable should not be recorded on AE pages of the CRF. Changes in a chronic condition of disease that are consistent with natural disease progression are NOT adverse events and also should not be recorded on the AE pages of the CRF.

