8.3 SAFETY

AEs, SAEs, and other findings will be summarized by presenting the percentages of subjects with each event. Continuous endpoints will be summarized using summary statistics such as means, medians, standard deviations, minima, maxima, and relevant percentiles.

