1.3.3 Safety Endpoints

The safety endpoints for this analysis include frequency, intensity, and relationship to study drug of adverse events and serious adverse events.

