6.2 Anticipated Adverse Events

Adverse events that are anticipated will be summarized by SOC, PT. An adverse event is considered anticipated based solely on the CRF field that captures if the adverse event is expected.

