Table 6.2.1	Summary of Maximum Corneal Curvature in Patients < 22 Years Old	Efficacy Analysis Set
Figure 6.2.1	Mean +/- SE of Maximum Corneal Curvature in Patients < 22 Years Old	Efficacy Analysis Set
Table 6.2.2	Analysis of Changes in Maximum Corneal Curvature in Patients < 22 Years Old	Efficacy Analysis Set
Table 6.2.3	Categorical Shifts in Maximum Corneal Curvature in Patients < 22 Years Old	Efficacy Analysis Set
Table 6.3.1	Summary of Maximum Corneal Curvature in Patients with Baseline Kmax ≥ 47	Efficacy Analysis Set
Figure 6.3.1	Mean +/- SE of Maximum Corneal Curvature in Patients with Baseline Kmax ≥ 47	Efficacy Analysis Set
Table 6.3.2	Analysis of Changes in Maximum Corneal Curvature in Patients with Baseline Kmax ≥ 47	Efficacy Analysis Set
Table 6.3.3	Categorical Shifts in Maximum Corneal Curvature in Patients with Baseline Kmax ≥ 47	Efficacy Analysis Set
Table 7.1	Overview of Adverse Events	Safety Analysis Set
Table 7.2	Treatment Emergent Adverse Events by SOC and PT	Safety Analysis Set
Table 7.3	Treatment Emergent Anticipated Adverse Events by SOC and PT	Safety Analysis Set
Listing 1	Subject Disposition	Treated Analysis Set
Listing 2	Listing of Patients with Re-Treatment with CXL	Treated Analysis Set
Listing 3	Listing of Aes	Safety Analysis Set

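### The interim SAP has no measurement-based safety output for IOP, slit lamp/haze or CDVA lines lost across all treated eyes, although the protocol names these as safety assessments

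*Protocol*

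**What the plan says.** Protocol 6.0 sets out the safety assessments: "Safety assessments include adverse events/serious adverse events, visual acuity loss, slit lamp findings, and intraocular pressure". Protocol 8.3 plans to report more than AEs: "AEs, SAEs, and other findings will be summarized by presenting the percentages of subjects with each event". It adds summary statistics for continuous endpoints. IOP, CDVA and a slit lamp exam with haze graded 0 to 4 are all required at Months 3 and 6 (protocol 5.4).

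The protocol also has a narrower list. Section 3.3 introduces its safety outcome measures with "Safety will be evaluated by assessing the following" and then names only AEs and SAEs.

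SAP 1.3.3 follows the narrower list: "The safety endpoints for this analysis include frequency, intensity, and relationship to study drug of adverse events and serious adverse events". SAP section 6 deals with AEs alone. In SAP Appendix B the safety outputs are Table 7.1 (overview of AEs), Table 7.2 (treatment-emergent AEs), Table 7.3 ("Treatment Emergent Anticipated Adverse Events by SOC and PT") and Listing 3 (AEs). SAP 1.6, on changes from the protocol, mentions the Month 12 estimate and the move to ANOVA, and says nothing about safety.

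Measured CDVA appears under efficacy, in the EAS (SAP 3.2.3 and 5).

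**The concern.** Three measured safety assessments have no safety output of their own, so the comparison of harm between the UVA groups depends on what investigators choose to report as an AE. The study is open label, so those reports come from sites that know the assigned exposure. By contrast, protocol 8.1 has CDVA read by a masked observer. The less bias-prone measurement is the one not used for safety.

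The interim results go to an FDA meeting on Phase 3 design, and the three groups differ in irradiance, duration or total dose. If an arm has more eyes with raised IOP, haze or lost lines, and some of these are not filed as AEs, the planned tables would not show it. A favourable mean CDVA change would not reveal it either.

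**Working it through.** The documents state no figure to reproduce. The check sets the passages side by side, and one illustration follows.

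**1. What each assessment in protocol 6.0 receives in the SAP**

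| Protocol 6.0 assessment | Collected at Months 3 and 6 | Output from the measurement | Output from AE reports |
|---|---|---|---|
| AEs/SAEs | not applicable | not applicable | Tables 7.1 to 7.3, Listing 3 |
| Visual acuity loss | CDVA, required | EAS efficacy summaries only; no count of eyes losing lines | if filed as an AE |
| Slit lamp findings, haze | required, haze 0 to 4 | none | if filed as an AE |
| IOP | required | none | if filed as an AE |

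**2. What the CDVA efficacy outputs cover.** The EAS is limited to keratoconus, no prior CK, no prior cross-linking, lenses removed per protocol, and a change from baseline in at least one efficacy endpoint. The protocol enrols seven diagnoses and allows repeat treatment after Month 6. Treated eyes outside the EAS have no acuity output. Inside it, primary and fellow eyes are summarised at Months 3, 6 and 12 with number, mean, SD, minimum, median and maximum (SAP 3.1, 5 and 5.1). A maximum shows one extreme eye; it does not count eyes past a threshold. SAP 5.2.2 does sort Kmax change into ten categories, but acuity has no equivalent.

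**3. Why AE tables are a weak substitute**

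- Protocol 6.1: "Changes in a chronic condition of disease that are consistent with natural disease progression are NOT adverse events". Protocol 6.3 lists disease progression as an anticipated AE, including a CDVA loss of more than two lines, and lists separately a CDVA loss of two or more lines. A three-line loss in a keratoconic eye fits both 6.3 entries, yet under 6.1 a site could leave it unrecorded.
- Events are counted once per subject (SAP 6.1.1), so the number of affected eyes cannot be recovered from the tables.
- For patients treated more than once, events are attributed to the last treatment received (SAP 6.1.3). SAP 2.3 says later procedures were re-randomized, so an event in one eye can be counted under the arm given to the other.
- Nothing is derived from measured values: "An adverse event is considered anticipated based solely on the CRF field that captures if the adverse event is expected".

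**4. Illustration: can a favourable mean coexist with eyes that lose vision?** Inputs, all assumed: normally distributed change, mean m, SD s, and a loss of 0.20 logMAR standing for two lines.

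P(loss of 0.20 or more) = 1 - Φ((0.20 - m)/s)

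| Assumed mean m | s = 0.10 | s = 0.15 | s = 0.20 |
|---|---|---|---|
| -0.05 (gain) | z = 2.50, 0.6% | z = 1.67, 4.8% | z = 1.25, 10.6% |
| 0 | z = 2.00, 2.3% | z = 1.33, 9.1% | z = 1.00, 15.9% |

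**5. Two lines needs a definition.** With the SAP 1.3.1 conversion, 20/20 to 20/30 is log10(30/20) = 0.176, and 20/20 to 20/32 is log10(32/20) = 0.204. A cut at 0.20 would count the second and miss the first.

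**The case against.** The other side has five good arguments.

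- **The SAP matches protocol 3.3.** That section names only AEs and SAEs as safety outcomes. This stands: the protocol disagrees with itself (3.3 against 6.0 and 8.3). The SAP also cites protocol Version 4.3, while the protocol supplied is headed 04.1 with a revision history ending at 04.2. A reader might infer that the SAP silently departed from its governing protocol; these documents cannot establish that.
- **The harms are reportable.** Protocol 6.3 lists CDVA loss of two or more lines, elevated IOP and haze as anticipated AEs, and 6.2 requires all AEs to be recorded. Once filed, they reach Table 7.2, and Table 7.3 if marked expected. A reader might infer that harmed eyes are invisible, or that these harms appear in no planned table. Neither is supported. Under-reporting is a risk, not a documented fact, and 6.1 does not tie the progression exemption to IOP or haze.
- **CDVA is more than a mean.** EAS summaries include spread and extremes for both eyes. This stands, but gives no count and leaves out treated eyes outside the EAS.
- **The scope is interim.** SAP 2.2 uses select CRF pages, SAP 3.2.3.1 tests no hypotheses, and a later SAP could add the tables. This lowers the weight of the point. It does not remove it, because the interim is what informs the Phase 3 design.
- **The percentages are assumed.** This stands. They run from 0.6% to 15.9% over the range shown, and a normal tail on whole-line Snellen data mixes measurement noise with true loss.

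**Conclusion.** The gap is real but bounded. For IOP and slit lamp/haze it is complete: both are collected at required visits and named as safety assessments, and no SAP output uses the measured values. For visual acuity it is partial: there is no count of eyes losing lines and no acuity output outside the EAS, but EAS eyes do have descriptive summaries.

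The firm size is structural: three of the four assessments in protocol 6.0 have no measurement-based safety output. The share of eyes losing 0.20 logMAR or more is illustrative only, since it rests on an assumed mean, SD, normal shape and line definition. At a mean of -0.05 it is 0.6%, 4.8% or 10.6% for SD 0.10, 0.15 or 0.20.

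The change is a worthwhile, cheap improvement. Without it the interim can describe reported events by arm, but not measured harm by eye and arm.

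**What to change.** Add one Safety Set table by eye, treatment received and visit, for Months 3 and 6. Show Month 12 as available, with denominators: it is optional in the protocol, and only some patients return (SAP 1.1). The table should give:

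1. Eyes with CDVA loss of two or more lines, with the logMAR cut stated on the Snellen-converted scale.
2. Eyes meeting the full protocol 6.3 IOP definition, including the two-occasion and intervention conditions. The rise on two occasions spans visits, so report it per eye over follow-up.
3. Post-procedure haze grade. Protocol 5.4 specifies the 0 to 4 rating at follow-up but not pre-procedure, so a shift from baseline may not be available.

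If the sponsor prefers to wait, SAP 1.6 should say that these outputs are deferred to a later SAP.

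Separately, protocol 3.3 must be reconciled with 6.0 and 8.3 on what counts as a safety outcome, and 6.1 with 6.3 on whether progression is recorded as an AE.

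The cost is a little programming, some CRF pages beyond the select set in SAP 2.2, and the patient-number mapping that SAP 2.3 already calls for. The Month 3 and Month 6 measurements come from required visits.

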6.1 DEFINITIONS OF ADVERSE EVENTS

An adverse event is any untoward and unintended sign, symptom or disease temporally associated with the use of an investigational drug or device, or other protocol-imposed intervention, regardless of the suspected cause. Conditions or diseases that are chronic but stable should not be recorded on AE pages of the CRF. Changes in a chronic condition of disease that are consistent with natural disease progression are NOT adverse events and also should not be recorded on the AE pages of the CRF.

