6.1.2 Unanticipated Adverse Device Effects (UADE)

An unanticipated adverse device effect (UADE) is any serious adverse effect on health or safety or any life-threatening problem or death caused by or associated with a drug or device, if that effect, problem, or death was not previously identified in nature, severity or degree of incidence. Anticipated adverse events are identified in Section 6.3. UADEs also include any unanticipated sight-threatening events and any other unanticipated serious problem associated with a device that relates to the rights, safety, or welfare of subjects.

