6.2 ADVERSE EVENT ASSESSMENT AND DOCUMENTATION

All subjects who have been exposed to the study treatment will be evaluated for adverse events. All adverse events, regardless of severity and whether or not they are ascribed to the study treatment, will be recorded in the source documents and CRF using standard medical terminology.

All adverse events will be evaluated beginning with onset, and evaluation will continue until resolution is noted, or until the investigator determines that the subject's condition is stable. The investigator will take appropriate and necessary therapeutic measures required for resolution of the adverse event. Any medication necessary for the treatment of an adverse event must be recorded on the concomitant medication case report form.

All AEs will be characterized by the following criteria:

- Date of onset
- Event diagnosis
- Intensity or severity
- Expectedness
- Relatedness to study treatment
- Treatment or action taken.
- Outcome

Whenever possible, recognized medical terms should be used when recording AEs. Colloquialisms and/or abbreviations should not be used. Only one medical concept, preferably a diagnosis instead of individual symptoms, should be recorded as the event.

If more than one distinct adverse event occurs, each event should be recorded separately. However, if known at the time of reporting, a diagnosis (i.e., disease or syndrome) should be recorded on the CRF rather than individual signs and symptoms. However, if a constellation of signs and/or symptoms cannot be medically characterized as a single diagnosis or syndrome at the time of reporting, each individual event should be recorded as a separate AE. A diagnosis that is subsequently established should be reported as follow-up information. However, signs and symptoms that are considered unrelated to an encountered syndrome or disease should be recorded as individual AEs.

Adverse events occurring secondary to other events (e.g., sequelae) should be identified by the primary cause; a "primary" event, if clearly identifiable, should represent the most accurate clinical term to record as the AE event term. For example:

Orthostatic hypotension ⇒fainting and fall to floor ⇒head trauma ⇒neck pain

The primary event is orthostatic hypotension and the sequelae are head trauma and neck pain.

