6.2.2 Expectedness

All AEs will be evaluated as to whether they are expected or unexpected.

- Expected (anticipated):** An adverse event is expected when the nature, severity, or degree of incidence was previously described. Expected adverse events are listed in 7.3.
- Unexpected (unanticipated):** An adverse event is unexpected when the nature, severity, or degree of incidence was not previously described.

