6.3 ANTICIPATED ADVERSE EVENTS

Epithelial Defect – A breach in the corneal epithelium that does not heal within 24 hours.

Persistent Epithelial Defect - A breach in the corneal epithelium that does not heal within 2 weeks.

Significant Decrease in Visual Acuity – loss of ≥ 2 lines CDVA

Sterile Infiltrates – Gray-white lesions caused by acute immune response to corneal damage.

Central Stromal Scars – New, significant corneal opacity in the central stromal region.

Corneal Haze – Cloudy or opaque appearance of the cornea. Grade Scale: 0 = clear cornea; 1 = focal areas of minimal stromal clouding or reticulation; 2 = diffuse mild stromal clouding or reticulation; 3 = Diffuse stromal clouding or reticulation somewhat obscuring the iris details; 4 = focal or diffuse areas of dense stromal haze obscuring iris detail.

Infectious Keratitis – Microbial infection of the epithelium or stroma.

Corneal Melt – A progressive, rapidly expanding, erosive, non-infectious, corneal ulcer.

Non-Infectious Keratitis – Inflammation of the cornea not associated with an infection.

Eye Pain – Eye pain lasting for >5 days.

Conjunctiva Hyperemia – Eye redness.

Foreign Body Sensation – Patient reports a feeling of a foreign body (e.g. gravel or sand) in the eye lasting >24 hours.

Corneal Hydrops – Acute corneal edema caused by a break in Descement membrane.

Herpes Simplex Virus (HSV) Reactivation – Epithelial keratitis, stromal keratitis, or disciform edema proven or clinically diagnoses as being caused by HSV.

Disease progression – Increase of $\geq 4D K_{max}$ as assessed by topography or tomography or loss of > 2 lines of CDVA.

Photophobia – Sensitivity to light lasting > 24 hours.

Elevated Intraocular Pressure (IOP) – IOP ≥ 30 mmHg or an increase in IOP of ≥ 10 mm from baseline recorded on two separate occasions or an increase in IOP that requires intervention.

Dry Eye Syndrome (DES) – Irritation of corneal surface due to inadequate production of tears that is consistently worse than the patient's pre-procedure state longer than 3 months after the cross-linking procedure.

Endophthalmitis – Diffuse intraocular inflammation predominantly involving the vitreous cavity but also involving the anterior chamber, implying a suspected underlying infectious cause.

Iritis – Presence of inflammatory cells in the anterior chamber. The presence of aqueous flare alone is not considered to constitute iritis.

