1. INTRODUCTION

CXL intends to utilize data from the ongoing CXL-005 Phase 2 clinical study to support the design of a Phase 3 trial. In preparation for a meeting with the FDA to propose the Phase 3 design, interim data from CXL-005 will be analyzed to help design the Phase 3 protocol. This version of the SAP describes the analyses planned to support the meeting with FDA.

This SAP is based on Version 4.3 of the study protocol dated 05-May-2017. Should the SAP and the protocol be inconsistent with respect to the planned analyses, the language of the SAP is governing. All analyses will be conducted using SAS version 9.4.

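### Protocol 6.1 and 6.3 leave open whether threshold-level disease progression goes on the AE pages, and no interim SAP table counts it from measured Kmax and CDVA

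*Protocol*

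**What the plan says.** Protocol 6.1 states that "Changes in a chronic condition of disease that are consistent with natural disease progression are NOT adverse events" and tells sites not to enter them on the AE pages of the CRF. It gives no dioptre or line limit.

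Protocol 6.3 lists Disease progression among the anticipated adverse events and defines it as a Kmax increase of 4 D or more "as assessed by topography or tomography or loss of > 2 lines of CDVA". The same list has a separate entry, "Significant Decrease in Visual Acuity", for a loss of 2 or more lines of CDVA. Protocol 6.0 names visual acuity loss as a safety assessment alongside adverse events, and 8.3 promises percentages for AEs, SAEs and further findings.

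In the interim SAP, section 1.3.3 limits the safety endpoints to AEs and SAEs. Section 6.2 says: "An adverse event is considered anticipated based solely on the CRF field that captures if the adverse event is expected". Section 5.2.2 sorts Kmax changes into categories whose top one is open at 2 D or more. Section 5.1 analyses CDVA as mean LogMAR change. Appendix B places every Kmax and CDVA table in the Efficacy Analysis Set (EAS).

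On versions, the SAP says: "This SAP is based on Version 4.3 of the study protocol dated 05-May-2017". The protocol supplied is headed Revision 04.1, with a revision history to 04.2.

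**The concern.** Most of the enrolled conditions are progressive, so worsening after treatment is a foreseeable outcome. One section tells the investigator that natural worsening is not an adverse event; another names worsening as one. An investigator who sees a Kmax rise of 4 D or more must decide, without a stated rule, whether it is natural progression that stays off the AE page or an anticipated event that goes on it.

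The AE tables could then understate progression by an amount that depends on individual judgement. Those tables matter: Protocol 7.0 makes the incidence or severity of adverse events a ground for stopping, and SAP section 1 says this package supports a meeting with FDA on the Phase 3 design. The trial is open label, and Protocol 8.1 describes masking only for the CDVA observer, not for whoever decides whether a change is natural progression.

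**Working it through.** No arithmetic applies. The check sets the passages side by side and then goes through the SAP output list.

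1. **Do 6.1 and 6.3 connect?** Section 6.1 excludes by the cause of a change (natural progression) and sets no limit. Section 6.3 includes by the size of a change (at least 4 D, or more than 2 lines) and is silent on cause. Sections 6.2, 6.2.2, 6.2.3 and 8.3 do not say which applies when a change meets both descriptions. Section 6.2 requires all adverse events to be recorded whatever their cause, but 6.1 decides what counts as one.

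2. **Is the CDVA limb covered another way?** In part. Any eye losing more than 2 lines also meets the entry for a loss of 2 or more lines, which is not labelled progression. Two things weaken this. Section 6.1 could be applied to that loss as well. And 6.2 says "Only one medical concept, preferably a diagnosis instead of individual symptoms, should be recorded as the event", which may steer an investigator towards the progression diagnosis. The Kmax limb has no such second entry, so it is the more exposed.

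3. **Can an unrecorded event reach the AE outputs?** No. Tables 7.1 to 7.3 and Listing 3 use events as recorded, and anticipated status comes from the CRF field rather than from the 6.3 definitions.

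4. **Do the measured-data tables count the 6.3 thresholds?** Only Tables 6.1.3, 6.2.3 and 6.3.3 count patients by size of change. Their top Kmax category pools rises from 2 D to just under 4 D with rises of 4 D or more, so it bounds the 4 D count from above without giving it. No output counts lines of CDVA lost. The maxima required by SAP 3.1 could at most show that some eye crossed a threshold, not how many did. Number of outputs counting a 6.3 progression or line-loss threshold from measurements: 0.

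5. **Who falls outside the measured-data tables?** SAP 3.2.3 removes every diagnosis other than keratoconus. It also removes keratoconus patients with prior CK, prior cross-linking, contact lenses not removed per protocol, or mismatched diagnosis records. In this package, progression or acuity loss in these patients can appear only through the AE outputs, although Protocol 6.0 names acuity loss as a safety assessment.

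6. **Can the size be computed?** No. The documents give no progression rate, no interim sample size and no information on how investigators read 6.1.

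One clerical slip does not alter the point: 6.2.2 says "Expected adverse events are listed in 7.3", whereas 6.1.2 has it right: "Anticipated adverse events are identified in Section 6.3".

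**The case against.** The strongest reply is that 6.1 is general and 6.3 specific, so 6.3 governs. Other 6.3 entries set limits on common findings in the same way (eye pain beyond 5 days, photophobia beyond 24 hours, dry eye beyond 3 months). Applying 6.1 to every case would leave the Disease progression entry with no effect. This is a sensible reading, and a reader who infers a flat contradiction goes too far. What remains is that no supplied text states this reading, while the instruction in 6.1 to keep such changes off the AE pages is explicit.

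Second, Protocol 8.3, read with 6.0, gives the protocol's own analysis a route to report acuity loss outside the AE pages, and Protocol 8.0 and 8.1 include all treated eyes. That stands. The table gap belongs to this interim SAP, and a reader should not infer that the final analysis will omit these counts.

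Third, this SAP is descriptive, uses selected CRF pages (2.2) and tests no hypotheses (3.2.3.1). That lowers the stakes, but a package meant to inform Phase 3 design still benefits from a safety count that does not depend on AE-page judgement.

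Fourth, the SAP was written for protocol Version 4.3, which may have changed 6.1 or 6.3. This cannot be settled from the supplied text, so the wording half of the point is conditional. The table half is not, because the SAP is itself based on 4.3 and contains no such table.

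**Conclusion.** The point holds in a limited form. In the supplied protocol text, 6.1 and 6.3 can be reconciled but are not, so recording of threshold-level progression may vary by investigator, with the Kmax limb more exposed than the CDVA limb. The interim SAP has no count from measurements that would make up for it, and for treated patients outside the EAS the AE outputs are the only place such events could appear.

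The size is unknown, and any figure for missed events would be pure assumption. A reader might infer that the AE comparison between groups is biased. The documents do not support that: randomization is stratified by site, which makes similar recording across groups plausible, and nothing shows that recording differs by group. The open-label design means only that this is not assured. The primary endpoint is measured CDVA and is unaffected.

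The conclusion assumes that Version 4.3 did not reconcile the two sections; if it did, only the missing table remains.

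**What to change.** 1. **Protocol.** Check Version 4.3. If 6.1 and 6.3 are unchanged, reconcile them so that one recording instruction applies to events meeting a 6.3 definition. Which clinical rule to adopt is not for this review. The 6.2.2 pointer can be corrected at the same time.

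2. **Interim SAP, whatever Version 4.3 says.** Add one descriptive safety table for all treated eyes, by treatment received and diagnosis, at Months 3 and 6, and at Month 12 where attended, with the number of eyes assessed at each visit.
   - Rows: Kmax increase of 4 D or more; CDVA loss of 2 or more lines; CDVA loss of more than 2 lines.
   - Count lines by a chart sequence stated in the SAP, because SAP 1.3.1 says letters read were not captured.
   - Use the baseline before the procedure being evaluated. Protocol 5.4 and SAP 2.3 allow repeat CXL under a new patient number with re-randomization, so count each treatment course of such an eye separately, under the treatment received, and flag it.
   - Footnote eyes whose contact lenses were not removed per protocol, and post-RK eyes with fluctuating vision.
   - State that the table covers these visits only. It does not capture events seen only at other optional or unscheduled visits, or in subjects without these visits.

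The cost is one extra table, from Kmax and CDVA data that Protocol 5.4 already requires at Months 3 and 6, and a wording clarification to the 21 sites. The clarification will not harmonise events already recorded; the table makes up for that only at the visits it covers.
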